Consultation findings will be discussed with the YPAG for interpretation, particularly to resolve divergent views. An additional output will be building a network of diverse audiences with whom we should be engaging when sharing learning from this study and developing the full trial.

We will examine: 1) Numbers of young women (including demographic characteristics) referred to and accessing school and non-specialist community mental health support. 2) Recruitment pathways for the full trial and other personalised public mental health interventions. 3) Young women's views on: acceptability of the intervention; potential intervention outcomes, mechanisms, and time to impact; reasons for non-adherence; optimal dose (e.g., how many videos to present); measures (including those sensitive to the needs of marginalised young women). 4) Implementation barriers/facilitators (research/intervention); 5) Intervention resource implications for future health economics. 6) Suggestions for the full trial and interest in taking part. 7) Any longer term impacts they envisage (e.g., staying in school) and what might happen without the intervention and not having needs identified and met at an early stage.

At this stage, our working design of the full trial is:

Population: Young women living in England aged 12-24; recruitment strategy and sample size calculation based on oversampling of the identified marginalised groups so we are powered to detect subgroup differences as well as whole sample differences. Young

women will be recruited through public and social media advertisements and through schools and community organisations, building on the networks of the applicants' and those extended during the present research. Prospective participants will be directed to the study website where they will record informed consent, be randomized, complete baseline measures, and then access either 'My Story and Me' or the leaflets (see below).

Intervention: 'My Story and Me'. The template for intervention description and replication (Hoffmann et al., 2014) will be agreed by the YPAG and Steering Group, based on learning from this development study, ahead of the full trial. It will be the basis of fidelity monitoring data collection.

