Comparator: Information leaflet on talking about mental health and expressing needs. As with 'My Story and Me', leaflets will be provided in range of formats (video, audio, text) and languages and participants will be able to choose different ones tailored to the needs of different ethnic, LGBTQI+, and neurodiverse groups.

Primary outcome: Mental health difficulties according to SDQ Total Difficulties (Goodman, 2001). Secondary mental health/wellbeing outcomes: PHQ-9 (Spitzer et al., 1999), GAD-7 (Spitzer et al., 2006), Warwick scale (Vaingankar et al., 2017); others TBC.

Study design: Pragmatic, single (researcher) blind RCT aligned to best practice (est. 36 months) (Schulz et al., 2010). Randomisation by independent Clinical Trials Unit. There will be an internal pilot with stop/go criteria.

Integration of quantitative and qualitative findings from RQ1-3

Two approaches will be used to combine the quantitative and qualitative analyses. The first is an explanatory sequential design for RQ 1 and 2 (Cresswell & Plano Clark, 2018). The quantitative findings from RQ 1 will identify mental health and wellbeing patterns for different groups of young women in the population and which multiply marginalised groups

to target for pre-recorded videos. This will inform the groups we interview in RQ 2, where we will examine the narrative experiences of young women aged 12-24 years in the community from diverse ethnic, LGBTQI+, and neuro-diverse groups about their mental health.

The second is a triangulation design convergence model for RQ 3 (Cresswell & Plano Clark, 2018). Quantitative and qualitative data will be collected from relevant stakeholders such as young women and education, mental health, and community organisations, through a survey and one-to-one or group discussions. Data will be analysed separately and then interpreted together to answer the question: what is the optimum approach to conduct (i.e., design and implement) the full trial of 'My Story and Me'?

Patient and Public Involvement

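### The working design for the full trial randomises participants before they complete baseline measures, so baseline scores and early drop-out are not protected from the allocation

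*Protocol*

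**What the plan says.** All of this comes from the Protocol, Study 3 (Plan the full efficacy trial), in the outline introduced by "At this stage, our working design of the full trial is".

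- **Entry.** Recruitment is by public and social media advertising and through schools and community organisations. "Prospective participants will be directed to the study website", "where they will record informed consent, be randomized, complete baseline measures, and then access either" the intervention or the comparator leaflets. The order is consent, randomisation, baseline, access. No other section gives a different one.
- **Blinding.** The Study design paragraph reads "Pragmatic, single (researcher) blind RCT aligned to best practice". Participants are not said to be blinded.
- **Primary outcome.** "Mental health difficulties according to SDQ Total Difficulties". The methods for Study 1 describe the SDQ as self-reported.
- **Allocation.** "Randomisation by independent Clinical Trials Unit". The outline names no stratification factors and does not say when a participant learns her arm.
- **Subgroups.** Recruitment and sample size are to rest on "oversampling of the identified marginalised groups so we are powered to detect subgroup differences as well as whole sample differences".

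**The concern.** A baseline measure is useful because allocation cannot have influenced it. When it is collected after randomisation, that protection depends on the participant not knowing her arm, and the outline does not secure this. A young woman who knows she will receive the videos, or only a leaflet, may rate her difficulties differently or may abandon the form. Either response could differ by arm.

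Three things are at stake:

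- the validity of baseline SDQ as a covariate or as the starting point for change;
- whether everyone randomised contributes at least some data;
- what information is available to the randomisation system when it allocates.

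**Working it through.** The Protocol gives no sample size, effect size, SD, power, correlation or drop-out rate for the full trial, so it has no figure to reproduce. The argument rests on the order of steps. The numbers below are illustrations on assumed inputs.

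**1. What follows from the order, by when the allocation becomes known**

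| | Allocation known or guessed before baseline | Allocation hidden until access |
|---|---|---|
| Baseline score | May be affected by arm | Not affected by arm |
| Leaving during the baseline form | May differ by arm | Balanced between arms in expectation |
| Status of those who leave | Randomised, no questionnaire data | Randomised, no questionnaire data |
| Stratifying on items first recorded at baseline | Impossible | Impossible |

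The last two rows hold in both cases. The first two depend on a fact that the Protocol does not state.

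**2. Bias if allocation shifts baseline reporting**

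Let b be the allocation-induced difference in mean baseline score (intervention minus control, in SD units) and ρ the baseline-to-outcome correlation. Assume equal SDs at both times, so that the regression slope equals ρ, and assume that the shift does not carry into the outcome. A baseline-adjusted analysis subtracts ρ × b from the outcome difference, so the bias is −ρ × b. Its size is:

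| ρ (assumed) | b = 0.05 | b = 0.10 | b = 0.20 |
|---|---|---|---|
| 0.4 | 0.02 | 0.04 | 0.08 |
| 0.6 | 0.03 | 0.06 | 0.12 |
| 0.8 | 0.04 | 0.08 | 0.16 |

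The range is 0.02 to 0.16 SD. Its direction depends on the sign of b, which the documents do not allow one to predict.

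**3. Participants randomised without data**

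Assume two-sided alpha 0.05, 90% power, 1:1 allocation and a standardised effect d. Then n per arm = 2(1.960 + 1.282)² / d². For d = 0.2 this is 2 × 10.51 / 0.04 = 525.5, rounded up to 526 per arm, or 1052 in total. Dividing by one minus the assumed loss and rounding up gives:

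| Lost during the baseline form (assumed) | Must consent | Randomised without data, current order | Randomised without baseline data, baseline first |
|---|---|---|---|
| 10% | 1052 / 0.9 = 1169 | 1169 − 1052 = 117 | 0 |
| 20% | 1052 / 0.8 = 1315 | 1315 − 1052 = 263 | 0 |
| 30% | 1052 / 0.7 = 1503 | 1503 − 1052 = 451 | 0 |

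The number who must consent is the same under either order. What changes is whether the loss falls before or after randomisation.

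**The case against.** The strongest reply is that this is a provisional sketch. The present project randomises no one, Study 3 exists to consult on the design, funding for the trial is still to be sought, and an independent Clinical Trials Unit will run the randomisation. That stands, and it lowers the urgency. It does not make the stated order sound, and the Protocol gives no reason for randomising first.

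Four stronger readings are tempting but not supported:

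- **That randomisation cannot be stratified on the oversampled groups.** The Protocol does not say when ethnicity, LGBTQI+ or neurodiverse status is recorded. It could be taken at eligibility or consent, and oversampling may itself require it at entry. Only stratification on items first recorded at baseline is ruled out: baseline SDQ, for example, and group identity if it is recorded only there.
- **That the primary analysis will be biased.** No analysis model is named for the full trial, and that is commonly left to the SAP. The bias also requires the allocation to be known or guessed before baseline. Access to the material comes only afterwards, and researcher-only blinding does not settle when participants learn their arm.
- **That early loss will differ by arm.** If allocation is hidden until access, leaving the form cannot depend on it, and excluding those people would not be expected to bias the comparison.
- **That the order inflates recruitment.** It does not, since the same number must consent either way.

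**Conclusion.** The order of steps is stated plainly and is the weaker choice for an unsupervised online trial with a self-reported primary outcome and no stated blinding of participants.

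Two consequences hold regardless of when allocation is revealed: people can be randomised and leave with no questionnaire data, and baseline-only items are unavailable for stratification. Two more, contaminated baseline scores and drop-out that differs by arm, are conditional on the allocation being known or guessed before baseline is complete.

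The possible bias of 0.02 to 0.16 SD rests wholly on the assumed correlation and shift and on an assumed baseline-adjusted analysis. It shows what could be at stake and is not an estimate for this trial. Because the design is still a working one, this is a point that should be corrected before the full-trial protocol is fixed, not a defect that invalidates the present studies.

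**What to change.** Restate the website sequence in the Population paragraph as: consent; eligibility and group identity; baseline measures; randomisation; access to the allocated material. This makes baseline scores pre-randomisation by construction, moves loss during the form ahead of randomisation, and allows stratification on the oversampled groups.

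If the present order is kept for a practical reason, the text should give that reason, state that allocation is concealed from the participant until baseline is complete, and state that group identity is recorded before randomisation. That would deal with the conditional risks but would still leave some randomised participants with no data.

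The cost is a change to the planned website flow and a sentence in the working design. Slightly fewer people reach randomisation, but all who do have baseline data.

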Appendix

Figure 1. Logic model with colour.

Figure 2.

Logic model without colour.
